Permuted block randomization with varying block sizes of 2 and 4 will be used to randomize 100 patients 1:1 to either the intervention or the control group. Random assignment will be conducted using the Statistical Analysis Software (SAS). Given the nature of the intervention, study participants and personnel will not be blinded to group allocation, but data analysts will be.

Intervention

Usual care

At discharge, patients will be provided with a written discharge prescription to be filled at their community pharmacy, and may or may not receive written or verbal instructions about changes made to therapy.

Intervention arm

At discharge, patients (and/or caregivers) will receive access to a medication management application that has been developed by the McGill Clinical and Health Informatics (MCHI) Research Group. The application will retrieve all medications prescribed to patients at discharge from an electronic form with structured data fields that has been completed by a study field coordinator using the patient's discharge prescription. The app will then generate a patient-friendly medication list and will offer a number of important features aimed at addressing barriers to adherence, including:

- **Pill identification:** This feature displays an image of a pill next to each medication in the list, with the intention of ensuring patients take the correct medications at the appropriate dosage and at the right times.
- **Drug information:** Patient-friendly monographs are provided to help patients and caregivers understand the indications for treatment, as well as the harms and benefits of their medications. Improved health literacy with respect to treatment has the potential to increase appropriate utilization of medications by patients.
- **Drug alerts:** Using prescription claims data of the 30 days post-discharge, which will be obtained from the RAMQ, this feature alerts patients to their non-adherence, such as in cases in which they have filled prescriptions that were stopped at hospital discharge, have yet to fill prescriptions for medications newly prescribed at discharge, or have been dispensed medications at the incorrect dose.
- **Daily pill reminders:** This feature reminds patients to take their medication on the day/time they are supposed to. Patients can choose whether or not they want this feature activated.

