- **Weekly dosing schedule:** This feature presents patients with an easy-to-interpret schedule of which medications need to be taken and when (with special instructions, e.g. needs to be taken with food). Medication names are displayed with images of the corresponding pill to prevent mix-ups.
- **Symptom checker:** This feature allows patients to enter their symptoms into the application and

determine which of the medications they are taking has side-effects similar to those they are experiencing.

- **Rate my med:** This feature allows patients to rate the medications they are taking (1-5 stars) and comment on how effective they have been or if they have experienced any negative side-effects. Patients can also view ratings given by other patients using the application for medications they have been prescribed.
- **Caregiver connect:** This feature provides the patient's caregiver(s) with access to their medication lists, as well as notifies them of nonadherence to treatment changes, with the aim of reducing its occurrence. Caregivers will have access to all the same information that patients have access to through the app.
- **Pharmacy connect:** This feature allows patients to connect with their hospital pharmacist and ask any questions they might have regarding their discharge prescription, therapy changes, and drug alerts. Based on their communication with the patient, hospital pharmacists then have the option to (1) recommend a course of action to the patient regarding their medications, (2) consult with the attending physician who was on duty at the time of the patient's discharge regarding a potential change in the patient's prescription, (3) contact the patient's community pharmacist to inform them of any errors in dispensation or any changes made to the patient's prescription, and (4) contact the patient's primary care physician, if and as needed.

Pilot-testing the app

Prior to enrolling patients in the study, we will pilot test the app using data from the RightRx study, which was also conducted in the internal medicine units of the MUHC (study #10-180 GEN). Anonymized data of RightRx patients will be fed into the app to test whether the app appropriately lists prescribed medications and generates the appropriate alerts for nonadherence. This process will help us identify any bugs in the app so that we can fix them prior to the app's use in the pilot trial.

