Pharmacy claims data from the RAMQ will be used to identify community medications dispensed to participating patients in the 30 days following hospital discharge. These data will be compared with the patient's hospital discharge prescription to identify non-adherence to in-hospital medication changes. Non-adherence to in-hospital treatment changes in the 30-day post-discharge period will be defined as (1) failure to fill newly prescribed medications, (2) re-filling a previous prescription that was stopped at discharge, or (3) filling a previous prescription whose dosage was modified at discharge, but was dispensed post-discharge at the incorrect daily dose.

Data sources

Prescription claims data from the *Régie de l'assurance maladie du Québec (RAMQ)* will be used to identify prescriptions filled in the 3 months prior to admission and the 1 year following discharge.

Medications prescribed at discharge and in-hospital medication changes will be determined using patients' discharge prescriptions, which will be obtained from patients' hospital charts.

Data Analysis

Descriptive statistics will be used to summarize demographic and clinical characteristics of the study population, results of the technology assessment questionnaire, and the frequency of nonadherence events (as defined in the previous section) in the 30 days post-discharge, overall and in each study group. We will then compare, between intervention and control groups, the average number of in-hospital medication changes not adhered to in the 30-day follow-up period using the Student's t-test. All quantitative statistical analyses will be conducted using SAS version 9.4. Data from the "think aloud" protocol will be analyzed qualitatively.

[figure not shown]
Project timeline

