The RCT will be conducted at the internal medicine unit of the Royal Victoria and Montreal General sites of the MUHC over a period of 1.5 years (Figure 2). Following approval of the study by the MUHC's institutional review board, study coordinators will begin recruiting, consenting, enrolling, and randomizing eligible patients who are admitted to the internal medicine unit of the MUHC Glen site. Based on recruitment rates from our recently completed trial which was also conducted at the MUHC, we expect this process to take approximately 5-6 months. At discharge, the study coordinator will provide enrolled patients in the intervention arm with access to the mobile application, enter their discharge prescription into the app, acquaint them with and train them in the various features of the app, and conduct a baseline usability assessment.

One week following discharge, study coordinators will conduct usability assessments at patients' homes. Assessment of non-adherence will be conducted by a data analyst at the MCHI Research Group using data from the RAMQ feed and patients' discharge prescriptions. Subsequent data analyses will be conducted over a period of 4 months, beginning 30 days following the enrollment of the last study patient. All data will be stored on a secure server at the MCHI centre, which can only be accessed using employee

identification cards. Following data analysis, an evaluation report will be disseminated to relevant stakeholders at the MUHC (e.g. Committee of Quality and Risk), and a manuscript will be prepared for potential publication in a peer-reviewed journal.

Figure 2. Gantt Chart.

Data storage, privacy, and confidentiality

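### Should non-adherence be scored against a prescription updated after discharge, given that Pharmacy Connect opens a route to changes in one arm only?

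*Combined protocol and SAP*

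**What the plan says.** Under Outcome measures, Non-adherence to treatment changes, dispensing in the 30 days after discharge is compared with the patient's "hospital discharge prescription to identify non-adherence to in-hospital medication changes". Three events count: a new drug not filled, a stopped drug refilled from an earlier prescription, and a dose-modified drug dispensed at the wrong daily dose. Data sources adds: "Medications prescribed at discharge and in-hospital medication changes will be determined using" the discharge prescriptions held in the hospital charts. Project timeline names the inputs to scoring: "Assessment of non-adherence will be conducted by a data analyst at the MCHI Research Group using data from the RAMQ feed", together with the discharge prescriptions. No later order is listed.

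Pharmacy Connect, described under Intervention arm, lets patients "ask any questions they might have regarding their discharge prescription, therapy changes, and drug alerts". The hospital pharmacist may then, among four options, "consult with the attending physician who was on duty at the time of" discharge about a possible change, or contact the community pharmacist to "inform them of any errors in dispensation or any changes made to the" prescription. The link to the hospital pharmacist runs through the 30 days and is replaced afterwards. Controls receive usual care without the app.

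Data Analysis compares the mean number of in-hospital changes not adhered to with one t-test and plans no sensitivity analysis.

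**The concern.** The intervention itself creates a route by which a discharge order can be legitimately altered during the outcome window, and the scoring rule does not mention it. If a new drug is cancelled before its first fill, a stopped drug is restarted before a refill, or a modified dose is revised again before dispensing, the patient may follow current instructions and still be counted as non-adherent. The reverse can also happen: a patient who ignores an authorised change and keeps to the discharge prescription is counted as adherent.

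Because the added route exists in one arm, these counts could differ between arms for reasons unrelated to adherence. The likelier direction is to understate the app's benefit. In a trial of 50 patients per arm, a few such events might seem enough to matter.

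**Working it through.** **1. Is the reference undefined?** The outcome definition, Data sources and Project timeline, read together, give one answer. The comparator is the discharge prescription, changes are identified as of discharge, and the analyst's inputs are claims and discharge prescriptions. An analyst following the text has no later order to apply. The rule is implied rather than spelled out, and it is the same in both arms.

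**2. Does a fixed reference suit the outcome?** The outcome is non-adherence to in-hospital changes. A new drug cancelled in the community is an in-hospital change that was not carried through. Such events are false only if the target is adherence to whatever prescription is currently in force, which is a different outcome.

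**3. How many events are exposed?**
- Consulting the physician is one of four pharmacist options, and the change must come before the dispensing that is scored.
- Alerts for a refilled stopped drug or a wrong dose follow the dispensing, so those events stand whatever is authorised later.
- The alert that can lead to an affected event is mainly the one for patients who "have yet to fill prescriptions for medications newly prescribed at discharge".
- The second and third event types refer to a previous prescription, and a newly authorised one is arguably not that, although the protocol does not say how claims would separate them.

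**4. Size.** The protocol gives no figure to reproduce here. Inputs:
- 50 per arm (100 randomised 1:1, Methodology).
- 54% of patients with at least one change not adhered to (Background, earlier trial), carried over to controls as an assumption.
- q = net excess of falsely counted over missed events per intervention patient, minus the same quantity in controls. It is assumed throughout and can have either sign.

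Control mean m from P(0) = 1 − 0.54 = 0.46:
- Poisson: m = −ln(0.46) = 0.777.
- Negative binomial with k = 1: m = 1/0.46 − 1 = 1.174.

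Standard error of the difference for a true 30% reduction:
- Poisson: √((0.777 + 0.544)/50) = 0.162.
- Negative binomial (variance m + m²): √((2.552 + 1.497)/50) = 0.285.

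Apparent reduction = 0.30 − q/m. Shift in standard errors = |q|/SE. Power is from 20,000 simulated trials, two-sided t-test at an assumed 0.05. Each cell gives Poisson / negative binomial.

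| q | Apparent reduction | Shift (SE) | Power |
|---|---|---|---|
| −0.05 | 36.4% / 34.3% | 0.31 / 0.18 | 41% / 29% |
| −0.02 | 32.6% / 31.7% | 0.12 / 0.07 | 34% / 25% |
| 0 | 30% / 30% | 0 / 0 | 29% / 22% |
| +0.02 | 27.4% / 28.3% | 0.12 / 0.07 | 25% / 21% |
| +0.05 | 23.6% / 25.7% | 0.31 / 0.18 | 20% / 18% |
| +0.10 | 17.1% / 21.5% | 0.62 / 0.35 | 12% / 13% |

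A q of 0.02 is one net event among 50 patients (0.02 × 50 = 1), and 0.10 is five. With no true effect and q = 0.05, two-sided rejection is 5.9% for an SD of 0.88 and 5.3% for an SD of 1.5, against a nominal 5%.

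**5. Would rescoring do better?** It needs dated authorised changes in both arms. App data exist for one arm only. No section says that pharmacist contacts are recorded, and community prescribers' changes in controls need not reach the hospital record. A common rule applied to unequal records would remove more events from the app arm.

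Never-filled drugs have no dispensing date. If they were judged at day 30, a drug left unfilled for three weeks and cancelled on day 22 after an alert would no longer count, although the delay was real. Only the app arm receives alerts, so this error also favours the app.

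**The case for a change.** The strongest case for a change is that the protocol foresees altered prescriptions, makes them easier in one arm, and neither states the scoring rule nor plans a check. An unstated rule leaves some discretion, and updating the reference only for changes known through the app would bias the result in its favour. A sentence, a count by arm and a supportive analysis look cheap.

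Part of this stands. The rule is not written out, the extra route is real, and at q = 0.10 the shift would not be trivial. The discretion is narrow, however: the listed inputs contain no later orders, and the protocol states that "study participants and personnel will not be blinded to group allocation, but data analysts will be". A count by arm would not be comparable, for the reasons in step 5. The supportive analysis would replace one rule applied equally with differential ascertainment, and it would need a contact log and a separate unblinded extract. Controls' prescriptions also change in ordinary care and are scored by the same fixed rule.

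**Conclusion.** No change to the plan is needed. The reference is fixed at discharge in both arms by the ordinary reading of the text, and this is defensible for non-adherence to in-hospital changes. Writing it out would alter no result. Pharmacy Connect may add some events that reflect an authorised change, most clearly a new drug cancelled before its first fill, but the number is unknown and the net direction uncertain.

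For an assumed |q| of 0.02 to 0.05, the shift is 0.07 to 0.31 standard errors. For a true 30% reduction, power is only 22% to 29% even at q = 0, so this point is not the main limit on interpretation. These figures rest on the 54% carried over from the earlier trial, the two assumed count distributions and the assumed q. The conclusion rests mainly on the fixed, symmetric reference and on the lack of comparable records for rescoring. The point can be mentioned as a limitation when results are reported.

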Evaluation of a Mobile Application to Enhance Medication Management Following Hospital Discharge

Research Protocol

April 26, 2019

[figure not shown]
NCT04676165

Background

Adverse drug events (ADEs) are among the leading causes of death in North America^{1,2}. Over 2 million ADEs occur each year, resulting in 100,000 deaths and \$36 million in economic costs³. In recently hospitalized patients, 70% of adverse events that occur within 30 days of discharge are medication related^{4,5}. Of these, at least 58% are preventable and tend to be the result of prescribing or dispensing errors, incomplete drug information, and underuse or overuse of medications^{6,7}.

A number of studies have demonstrated that patients are usually discharged from hospital on substantially different medication regimens than those prior to admission. However, discharge prescriptions are typically not well followed in the community post discharge. We have further explored this phenomenon through secondary analysis of data from a randomized controlled trial (RCT) recently conducted by our study team at the McGill University Health Centre (MUHC), which evaluated the impact of electronic medication reconciliation on ADEs post hospital discharge. Our analyses suggested that 54% of study patients were non-adherent to at least 1 in-hospital medication change, and that patients who were non-adherent to 4 or more in-hospital medication changes experienced a 64% increased risk of emergency department visits and hospital re-admissions compared to those who were adherent to all changes (Figure 1). Furthermore, analyses of patient interview data suggested that unclear communication with patients about medication changes and the reasons for these changes may be driving non-adherence, as might difficulties in managing complex drug regimen information and dosing schedules (data from in-progress manuscript). There is therefore a clear need to implement and evaluate patient support mechanisms that reduce non-adherence to essential changes in therapy following hospitalization.

Figure 1. Impact of non-adherence to in-hospital medication changes on ED visits and hospital re-admission 30 days post discharge.

Objective

The objective of this project is to evaluate the usability and efficacy of a mobile application aimed at improving medication management and subsequent adherence to in-hospital medication changes among high risk patients.

Methodology

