We will conduct an RCT that will assess the usability of a medication management mobile application and its efficacy in decreasing non-adherence to in-hospital medication changes among patients in the internal medicine ward of the Royal Victoria and Montreal General sites of the MUHC. One hundred patients will be randomized 1:1 to either the intervention arm, in which they will receive access to the mobile app, or the control arm, in which they will receive usual care (i.e., no medication management support). We will conduct a usability assessment at hospital discharge (baseline) and at 1 week post-discharge to obtain patient feedback on the app (via a technology acceptance questionnaire) and to document usability using the “think aloud” protocol^{8,9}. We will also compare, between the 2 arms, the rates of non-adherence to treatment changes in the 30-days post-discharge.

Study population

The study population will comprise 100 patients who are discharged from the internal medicine unit of the Royal Victoria and Montreal General sites of the MUHC. To be eligible for participation in the trial, patients must also be covered by the Quebec public insurance drug plan (i.e. they are 65 years or older, are recipients of social assistance, or do not have private drug insurance), must be 18 years or older at the time of admission, must own a tablet, smartphone, desktop PC, or portable computer, must have internet connection on their tablet/smartphone/laptop/PC, must speak and read either English or French, must not be discharged to a rehabilitation or long-term care center, and must have a prognosis of more than 3 months.

Patients who are cognitively impaired or otherwise unable to provide consent will be eligible for inclusion in the study if surrogate consent is granted by a legally authorized representative and if a caregiver has agreed to use the app on the patient’s behalf. Similarly, patients who are completely dependent on a caregiver but capable of providing consent will be enrolled only if the caregiver has agreed to use the app.

Participant recruitment, consent, and enrollment

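### The 30-day non-adherence count has no rule for death, readmission or facility entry before filling, so some new drugs are scored as unfilled for reasons other than adherence

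*Combined protocol and SAP*

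**What the plan says.** Under Outcome measures, Non-adherence to treatment changes, the source is community dispensing: "Pharmacy claims data from the RAMQ will be used to identify community medications dispensed to participating patients in the 30 days following hospital discharge". These claims are compared with the hospital discharge prescription. Three things count as events:

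- Component 1: "Non-adherence to in-hospital treatment changes in the 30-day post-discharge period will be defined as (1) failure to fill newly prescribed medications".
- Component 2: "2) re-filling a previous prescription that was stopped at discharge".
- Component 3: "filling a previous prescription whose dosage was modified at discharge, but was dispensed post-discharge at the incorrect daily dose".

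Data Analysis then compares "the average number of in-hospital medication changes not adhered to in the 30-day follow-up period using the Student's t-test". Project timeline says that a data analyst makes the assessment, and names two inputs: the RAMQ feed and the discharge prescriptions. No section gives a rule for a patient who dies, returns to hospital or enters a facility during the 30 days.

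Three other places bear on the point.

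- Study population says that patients "must not be discharged to a rehabilitation or long-term care center" and requires a prognosis of more than 3 months. Both criteria apply at entry only.
- The Background figure is titled "Impact of non-adherence to in-hospital medication changes on ED visits and hospital re-admission 30 days post discharge", so the team has studied return to hospital in this same window.
- Pharmacy connect, in the app arm only, lets the hospital pharmacist "consult with the attending physician who was on duty at the time" of discharge about a possible prescription change.

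**The concern.** Component 1 is an event defined by absence: no claim means non-adherent. That is sound only while the patient is at home and able to fill. A patient who dies or is back in hospital before filling has no claim for reasons unrelated to adherence, yet every unfilled new drug adds one to the count. Components 2 and 3 need a community fill, so the same patient has less opportunity to register them. After a readmission, a second discharge prescription may replace the first, but the comparison is still with the first.

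The count then mixes hospital use with adherence. Scoring a few patients at or near their full number of new drugs inflates the variance and weakens a test with 50 patients per arm. If the app changed early readmission, part of any arm difference would reflect hospital use. Separately, an app patient who follows a prescription changed through Pharmacy connect could be scored against the superseded list. The protocol creates that route in one arm only.

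**Working it through.** The plan gives no power calculation and no rate of readmission, death or facility entry, so there is no figure to reproduce. What follows is an illustration.

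**From the documents.** n = 50 per arm (100 patients, 1:1); 54% non-adherent to at least one change in the team's earlier trial (Background).

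**Assumed.** Counts are Poisson; the app truly halves the mean; two-sided 5% test; e = share of patients with an event by day 30; f = share of those events that come before filling with no later fill in the window; m = new drugs per patient. An affected patient scores m on component 1 and zero on components 2 and 3.

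**Step 1, baseline.** Mean λ = −ln(1 − 0.54) = 0.777 in control and 0.388 with the app; difference 0.388. Standard error = √((0.777 + 0.388)/50) = 0.153. Power ≈ Φ(0.388/0.153 − 1.96) = 72%.

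**Step 2, affected share and net rise in the control mean.** q = e × f. Because the affected patient's count is replaced and not added to, the net rise is q(m − λ).

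| e | f | m | q | Net rise | Share of 0.777 |
|---|---|---|---|---|---|
| 10% | 15% | 2 | 1.5% | 0.015 × 1.223 = 0.018 | 2% |
| 15% | 30% | 3 | 4.5% | 0.045 × 2.223 = 0.100 | 13% |
| 25% | 30% | 3 | 7.5% | 0.075 × 2.223 = 0.167 | 21% |

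**Step 3, power with equal q in both arms.** For an arm with mean λ, the observed mean is (1 − q)λ + qm, and the variance is (1 − q)(λ + λ²) + qm² − (observed mean)². The observed difference shrinks to (1 − q) × 0.388.

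| q | m | Variance, control | Variance, app | Difference | Standard error | Power |
|---|---|---|---|---|---|---|
| 1.5% | 2 | 0.787 | 0.421 | 0.382 | 0.155 | 69% |
| 4.5% | 3 | 0.954 | 0.664 | 0.371 | 0.180 | 54% |
| 7.5% | 3 | 1.061 | 0.832 | 0.359 | 0.195 | 45% |

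Simulated t-tests agree to within about one percentage point. The difference hardly moves; the variance causes the loss. If affected patients were simply left out, power would be about 71%, 70% and 69%. That is only a rough guide to what can be recovered, since the fix below sets aside drugs and not patients.

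**Step 4, bias between arms.** Suppose that the app has no effect on adherence but cuts these early events by a third. The spurious difference is (q/3)(m − λ) = 0.006, 0.033 and 0.056 changes per patient. Simulated false rejection stays between about 5% and 6%. A much stronger assumption (10% affected in control, 5% with the app, 4 new drugs each) gives 0.05 × (4 − 0.777) = 0.16 and false rejection of about 10%.

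**Step 5, Pharmacy connect.** If a share p of app patients had one superseded change wrongly counted, the observed difference would fall by p. At p = 5% it goes from 0.388 to 0.338. The documents give no value for p. This error works against the app.

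**The case against.** The protocol nowhere states that such patients are failures; it gives a general definition and is silent on them. That is fair as a description of the text, but it does not remove the problem. With two named inputs and no exception, an analyst who follows the definition literally has to score an unfilled new drug as non-adherent.

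A reader might infer that every patient readmitted, dead or moved within 30 days is scored as failing. The documents do not support this. A patient who fills before the event, or who comes home and fills within the window, is not affected. On the assumptions above, f is 15-30%, so 70-85% of patients with an event escape.

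A reader might also infer that the test is biased in favour of the app. That does not follow either. With equal event rates randomisation affects both arms alike, components 2 and 3 move the other way, and Pharmacy connect changes would count against the app.

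Other parts of the objection stand. Eligibility makes early death and facility entry less likely, which leaves readmission as the main route. The documents do not say whether RAMQ claims capture drugs supplied in a facility. Background gives only a relative increase (64%) for emergency visits and readmissions combined, and an emergency visit alone need not prevent a fill. If most new drugs are filled soon after discharge, the effect is negligible.

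**Conclusion.** The concern holds in a limited form. As written, the rule gives a wrong score to patients whose death, readmission or facility entry comes before filling and who do not fill later in the window. It also judges fills after a second discharge against a replaced list. The net direction depends on the mix of new, stopped and modified drugs.

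The main cost is power: from about 72% for a true halving to 69% at the low end of the assumptions and 45% at the high end. Every input except the 54% and the 50 per arm is assumed, including the Poisson shape, so the range matters more than any single figure. Bias between arms is small unless the app substantially changes early readmission. No figure in the protocol is contradicted. The change is still worth making, because this count feeds the only between-arm test.

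**What to change.** Amend Non-adherence to treatment changes, and Data sources to match:

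1. Assess each medication change from discharge to the earliest of day 30, death, readmission or facility entry.
2. Treat a new drug still unfilled at an early end as not evaluable, not as non-adherent. Report the number of evaluable changes by arm.
3. Do not judge fills after a second discharge against the first prescription.
4. Have the blinded analysts apply the same rule in both arms.
5. Do not use a days-in-community offset for component 1. Failure to fill becomes less likely with time, so it does not accrue in proportion to days observed.
6. Name the source of event dates. The data storage section already provides for data from hospital records, but Data sources names charts only for discharge prescriptions.
7. Report the count both ways and keep the as-written version. Background links non-adherence to readmission, so ending observation at readmission may be informative.
8. Record prescription changes made through Pharmacy connect, and add a sensitivity analysis that does not count them as non-adherence. State that equivalent changes in the control arm may not be seen, so this analysis ascertains changes unequally.

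The cost is a few sentences of protocol text and the collection of event dates. Some true early non-adherence will be set aside, and readmissions to other hospitals may be missed, so the correction is partial.

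### Non-adherence rule 1 makes no exception for as-needed drugs, and the alert for unfilled drugs reaches one arm only, so prompted but unneeded fills could favour the app (cheap improvement)

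*Combined protocol and SAP*

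**What the plan says.** The outcome is defined under Outcome measures, Non-adherence to treatment changes. Claims are used to "identify community medications dispensed to participating patients in the 30 days following hospital discharge", and then: "These data will be compared with the patient's hospital discharge prescription to identify non-adherence to in-hospital medication changes". Three events count. Rule 1 is "failure to fill newly prescribed medications". Rule 2 is refilling a drug that was stopped. Rule 3 is "filling a previous prescription whose dosage was modified at discharge, but was dispensed post-discharge at the incorrect daily dose". Data Analysis compares the mean number of changes not adhered to between arms with a t-test.

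Under Intervention arm, the drug-alert feature warns patients when they "have yet to fill prescriptions for medications newly prescribed at discharge" or "have been dispensed medications at the incorrect dose". The caregiver feature also passes on notices of non-adherence. Under Methodology, control patients have no app and so receive neither.

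No section mentions as-needed or variable-dose prescriptions, says how they are scored, or states how a daily dose is obtained from a claim.

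**The concern.** A dispensing claim shows that a drug was collected. It does not show whether the drug was needed or taken. For a drug taken on a regular schedule, not filling it is a reasonable sign that the change was not followed, and an alert that leads to a fill is the app working as intended. For an as-needed drug that link breaks, because a patient without the symptom can follow the prescription fully and never fill it. Rule 1 scores that patient as a failure and scores an unnecessary fill as a success.

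If this mis-scoring were the same in both arms it would only add noise. Randomization balances, on average, how many as-needed drugs are prescribed. It does not balance the prompt to fill them, which comes after randomization and goes to one arm. Keeping the data analysts blind does not help, because the claims themselves would differ. Any unneeded fill that an alert prompts lowers the intervention count, with no gain on the stated objective of better medication management and adherence.

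**Working it through.** **The text.** Outcome rule 1 and the alert for unfilled drugs describe the same event. Rule 1 applies to both arms, and the alert to one. Neither carries an as-needed exception. The possible bias follows from these two passages together and has one direction, towards the app.

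**Its size.** The plan has no figure to reproduce: the 100 patients are not accompanied by a significance level, power, target difference or SD. What follows is illustration.

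Inputs from the protocol:
- 100 patients allocated 1:1, so 50 per arm (Randomization and blinding).
- 54% of patients in the team's previous trial were non-adherent to at least one change (Background). This is used only to suggest an SD.

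Assumed inputs:
- New as-needed drugs per patient, a: 0.25 to 1.0.
- Share unfilled without alerts, u: 0.30.
- Share of those filled because of alerts, r: 0.25 to 0.50.
- Two-sided level 0.05, 80% power, normal approximation.
- No true effect on adherence.

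Spurious difference: d = a × u × r.
- Lowest: 0.25 × 0.30 × 0.25 = 0.019.
- Highest: 1.0 × 0.30 × 0.50 = 0.15.

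SD, assumed two ways:
- Poisson count with P(at least 1) = 0.54: mean = −ln(0.46) = 0.78, SD = √0.78 = 0.88.
- 1.5, to allow for overdispersion.

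Standard error of the difference = SD × √(2/50) = 0.2 × SD, which is 0.176 or 0.300. Detectable difference = (1.960 + 0.842) × SE, which is 0.49 or 0.84.

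Rejection rate = Φ(d/SE − 1.96) + Φ(−d/SE − 1.96).

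| a × u × r | d | SD 0.88: share of detectable difference; rejection rate | SD 1.5: share; rejection rate |
|---|---|---|---|
| 0.25 × 0.30 × 0.25 | 0.019 | 4%; 5.1% | 2%; 5.0% |
| 0.5 × 0.30 × 0.25 | 0.0375 | 8%; 5.5% | 4%; 5.2% |
| 0.5 × 0.30 × 0.50 | 0.075 | 15%; 7.1% | 9%; 5.7% |
| 1.0 × 0.30 × 0.50 | 0.15 | 30%; 13.6% | 18%; 7.9% |

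The result depends almost wholly on how common new as-needed drugs are and how readily patients act on the alerts. The protocol informs neither.

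**The case against.** Four arguments can be made for leaving the plan alone.

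- **The gap is one of silence.** The protocol never says that as-needed drugs are to be scored like scheduled ones, and an unwritten coding rule may exist. That is true, but rule 1 as written has no exception, and a rule that affects the main comparison should be on paper before analysis.
- **The alerts may not cause unneeded fills.** They may not fire for as-needed drugs, or patients may ignore them. The pharmacist-contact feature lets patients query an alert, and the planned pre-enrolment testing checks that alerts are appropriate. These points bear on how often unneeded fills would occur. They do not change how a fill is scored, so they lower the likely size without removing the mechanism.
- **Having the drug on hand could itself be counted as adherence.** That is a defensible definition. If the sponsor intends it, the protocol should say so, and rule 1 could then stand.
- **The effect may be trivial.** At the low end of the range it is.

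A reader might also infer that rule 3, with its test of "dispensed post-discharge at the incorrect daily dose", will misread correct tapers as wrong doses. The documents do not support that. Rule 3 covers only previous prescriptions whose dose was modified at discharge, so a newly started taper falls under rule 1, where filling it counts as adherence. No passage says that daily dose is quantity divided by days' supply. Even under that method, the prescribed taper averaged in the same way would match the dispensed one. An error arises only if an average is compared with a single step, which the plan does not prescribe, and any such error would be roughly equal between arms. What stands is narrower: the basis of the dose comparison is not stated.

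**Conclusion.** The concern holds for rule 1. Followed as written, the rule mis-scores as-needed drugs, and the intervention acts on the mis-scored event in one arm only. The between-arm difference could therefore favour the app without any gain in adherence. Under the assumed rates, the spurious difference is about 0.02 to 0.15 changes per patient. This is 4% to 30% of the detectable difference if the SD is 0.88, and 2% to 18% if it is 1.5.

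A reader might go further and conclude that the trial's result will be biased, or that a positive finding would be an artefact. The documents do not support that: every rate is assumed, and the low end of the range is negligible. For scheduled drugs, the overlap between alert and outcome is the intended mechanism and is no defect. The point is a cheap improvement to outcome scoring. It implies nothing about how any drug should be prescribed or used.

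**What to change.** In Non-adherence to treatment changes:

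- Leave as-needed lines out of rule 1 in the main count, and report the count with all lines included as a sensitivity analysis.
- Identify as-needed lines from the discharge prescription in the hospital chart, which Data sources already names as the source for determining changes. Use that source in both arms, because the structured electronic form is described only for the intervention arm. The coder should be unaware of allocation, which rules out the unblinded field coordinators. The blinded data analyst is one option.
- Keep as-needed lines in rule 3 wherever the strength can be compared, so that real dispensing errors still count.
- State for rule 3 that dispensed and prescribed regimens are compared on the same basis. Total quantity alone is not enough, since a flat and a stepped regimen can have the same total.

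The app's alert logic need not change. The cost is one coded field for each prescription line in both arms, a few sentences in the protocol, and slightly fewer scorable changes per patient. The main count would also miss as-needed drugs that were needed but not filled. The sensitivity analysis keeps them in view.
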